8.7.1. Cohort A: Negative Emotional Bias

Negative Emotional Bias, measured in the Facial Expression Recognition Task (FERT) and collected before dose on Day 1 and after dose on Days 7 and 14 for Cohort A subjects, will be summarized by disease criteria and treatment. Observed values and change from baseline will be summarized.

8.7.2. Cohort B: Cognitive Fluctuations

Cognitive fluctuations among Cohort B subjects are measured by spectral analysis of waking EEG, activity tracking, pupillometry, and DCFS. The observed values and change from baseline in overall values (spectral analysis, activity tracking, and pupillometry) or scales (DCFS) will be summarized by disease criteria and treatment.

8.8. Analysis of Secondary Endpoints

Secondary endpoints related to cognition, physiological symptoms, pupillary data, mood and sleep will be summarized by disease criteria, treatment and overall using the FAS. Select summaries may be repeated in the PPS. Comparisons between treatments will be performed similar to the analysis of primary endpoints. All data will be listed.

8.8.1. Cognition, Mood, and Physiological Symptoms

The absolute values and change (when applicable) from baseline in overall scores and sub-domain scores where applicable will be summarized for Verbal Fluency (alphabet & category), CANTAB, BioStamp, GDS and HADS.

8.8.2. Pupillary-Related Endpoints

Pupillary parameters measured using the pupillary light reflex test including pupil area, baseline pupil diameter (BPD), maximum constriction velocity (MCV), absolute constriction amplitude (ACA), maximum dilation velocity (MDV), time to reach 75 % of initial resting diameter during pupillary dilation ($T^{3/4}$), and average dilation velocity will be summarized by disease criteria, treatment and overall using the FAS.

8.8.3. Epworth Sleepiness Scale

The absolute values and change from baseline in overall scores will be summarized for ESS.

8.8.4. Analysis of Safety

Safety endpoints will be summarized by disease criteria, treatment and overall using the Safety Set. Additional summaries may be performed by treatment sequence and/or period. A limited set of endpoints may also be summarized using other analysis populations.

8.8.5. Adverse Events

All reported AEs will be coded using the Medical Dictionary for Regulatory Activities (MedDRA). Adverse event collection will begin during the Lead-In period and will be collected up to 14 days after the last dose of study drug. All AEs collected on/after first dose of study drug will be considered treatment emergent (TEAE). Each TEAE will further be attributed to a treatment (CST103/CST107 or placebo) based on the AE start date. If a TEAE start date is prior to the first dose in Treatment Period 2, the AE will be attributed to the treatment received in Period 1. If a TEAE start date is on/after to the first dose in Treatment Period 2, the AE will be attributed to the treatment received in Period 2.

An overall summary of the number and percentage of subjects experiencing TEAEs, serious AEs (SAEs), treatment-related AEs, AEs by maximum severity and AEs leading to treatment withdrawal will be provided. Treatment-emergent AEs, SAEs, and treatment-related AEs will be further summarized by MedDRA system organ class and preferred term and reported by treatment group.

The number and percentage of subjects with adverse events reported during the Lead-In period will also be summarized separately.

All AEs will be listed. Separate listings may be prepared for SAEs, AEs leading to study drug termination, and treatment-related AEs.

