- Assessment of concomitant medications

5.1.1.3. **Day 1, Treatment Periods 1 and 2**

The following procedures will be performed, and assessments/measurements recorded:

- Review of inclusion/exclusion criteria (Treatment Period 1 only)
- Assessment of concomitant medications
- Obtain bottle numbers (for CST-103 and CST-107) from the IWRS and dispense study medication
- Vital signs (BP, HR, respiration rate, and oral/tympanic temperature); BP and HR measurements obtained 3 times (separated by approximately 1 minute) after the subject is supine for 5 minutes:
 1. Prior to dosing (within 15 minutes)
 2. 1 hour (± 30 minutes) after dosing
- 12-lead ECG, obtained after subject has rested in supine position for at least 5 minutes:
 1. Prior to dosing (within 15 minutes)
 2. 1 hour (± 30 minutes) after dosing
 3. 4 hours (± 30 minutes) after dosing
- C-SSRS (not required during Treatment Period 1)
- Laboratory tests – subjects should be fasting for 8 hours prior to the safety labs
 - Hematology, chemistry, and urinalysis

- Serum or urine pregnancy test (per standard site practice) for females of childbearing potential; positive urine pregnancy result to be confirmed by serum test
- Alcohol test
- Blood sample collection for pharmacodynamic biomarkers
- Blood sample for APOE4 genetic test (Treatment Period 1 only; for ongoing subjects who have completed visits beyond Treatment Period 1, Day 1, the test may be done at any time during the study)
- PK samples:
 1. Prior to dosing
 2. 4 hours (± 10 minutes) post dose
- Pharmacodynamic sample collection prior to dosing
- FERT, administered prior to dosing
- CANTAB tests and verbal fluency test (alphabet & category):
 1. Prior to dosing
 2. 4 hours (± 30 minutes) post dose
- Pupillary light reflex (PLR) tests (twice for each eye):
 1. Prior to dosing
 2. After the post dose CANTAB
- HADS
- GDS
- ESS
- FOG-Q (RBD+PD subjects only)
- BioStamp dispensed – to be worn daily throughout each Treatment Period and removed on Day 14
- Administer study medication
- Provision of subject dosing diary
- Assessment of AEs
- Schedule Day 7 Visit

5.1.1.4. Day 7 (± 1), Treatment Periods 1 and 2

The following procedures will be performed, and assessments/measurements recorded:

- Assessment of concomitant medications
- Assessment of AEs
- Administer study medication and conduct a dosing compliance check

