6.1.2. Assessment of Adverse Events

Each event recorded on the AE CRF will be assessed by the Investigator with regard to the following categories.

Severity

Severity of AEs will be graded as one of:

- **Mild:** Awareness of signs or symptoms but easily tolerated. A type of AE that is usually transient and may require only minimal treatment or therapeutic intervention. The event does not generally interfere with usual activities of daily living.
- **Moderate:** A type of AE that is usually alleviated with additional specific therapeutic intervention. The event interferes with usual activities of daily living, causing discomfort but poses no significant or permanent risk of harm to the research subject.
- **Severe:** Incapacitating the ability to do work or to do activities. A type of AE that interrupts usual activities of daily living, or significantly affects clinical status, or may require intensive therapeutic intervention

Relationship to Study Medication

The Investigator or designee, using clinical judgment, will assess the causality/relationship between each AE and the most recently administered study medication (i.e., whether there is a reasonable possibility that the drug caused the event) and record that assessment in the CRF.

Unrelated: The AE is clearly not related to the study medication. The AE is clearly explained by another cause, or exposure to the study medication has not occurred.

Related: The AE may be related to the study medication. The AE and administration of the study medication are considered reasonably related in time, but the AE is more likely explained by the study medication than another cause.

AE reporting will extend from randomization until completion of the Follow-Up Visit. AEs occurring after the end of the clinical trial must be reported if the Investigator considers there is a causal relationship with the study medication.

All AEs, regardless of the relationship to study medication, will be recorded in the CRF.

All reports should contain a brief description of the event, date of onset, date of resolution, severity, treatment required, relationship to study medication, outcome, and whether the event is classified as serious. Whenever possible, the Investigator should group signs or symptoms that constitute a single diagnosis into a single event term. For example, “cough, rhinitis, and sneezing” might be grouped together as “upper respiratory tract infection.”

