## 6. GENERAL DATA HANDLING CONVENTIONS

### 6.1. Reference Dates

- Screening date is defined as the eCRF provided date on which a subject was screened for trial entry.
- Treatment start date is defined as the date of first dose of study drug. Each treatment period will have a treatment start date (i.e., in order to determine AEs occurring during a treatment).
- Treatment end date is defined as the date of last dose of study drug.
- Safety data, such as AEs and laboratory assessments will use the treatment start date as a reference date.
- Study day will be based on treatment start date as a reference date.

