### 6.3. Baseline and Post-Baseline Changes

Unless stated otherwise, baseline and post-baseline change values will be based on the following:

- Baseline will be based on the last non-missing value collected prior to or on the treatment start date and time. Post-baseline values will be those collected after the treatment start date and time.
- Change from baseline is defined as: value – baseline value.

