### 10.1. Adverse Events

Adverse events (AEs) will be recorded from the signing informed consent through end of study. AEs will also be assessed for severity, relationship to study drug, and seriousness. AEs will be considered treatment-emergent if their onset occurs following the date of first dose up to the study completion date. Each TEAE will also be categorized according to the treatment period in which it occurs, in order to attribute and summarize an AE based on treatment received at time of event (i.e., during placebo or active treatment). Events that occur during the washout period between Treatment Period 1 and 2 will be attributed to the treatment received in Period 1, and events occurring after Treatment Period 2 up to the End of Study visit will be attributed to the treatment received in Period 2.

Any missing severity assessments will be assumed to be severe, missing relationship assessments will be assumed to be related, and missing seriousness assessments will be assumed as serious.

An overview of AEs will be produced, including counts and percentages of subjects with any incidences of: treatment-emergent AEs (TEAEs), serious AEs (SAEs), related AEs, unrelated AEs, AEs by maximum severity, AEs leading to treatment withdrawal and AEs leading to death.

Sponsor: CuraSen Therapeutics, Inc.  
Protocol Number: CST103/CST107-CLIN-011  
Version and Date: [REDACTED] v1.0 / 24May2022

Adverse events will be coded based on the Medical Dictionary for Regulatory Affairs (MedDRA 23.1) for reporting by system organ class (SOC) and preferred term (PT) in descending order of overall incidence.

Summaries of adverse events by SOC and PT will include the following types:

- TEAEs;
- SAEs; and
- Related AEs.

A summary of TEAEs by SOC, PT, and maximum severity will also be prepared.

A comprehensive listing of all AEs will be provided in a by-subject data listing. In addition, the following listings will be provided:

- SAEs;
- Related AEs; and
- AEs leading to study drug termination

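### The date-based AE rule puts events arising before dosing on Period 2 Day 1 under the Period 2 treatment, contrary to the SAP's own washout rule

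*Protocol*

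**What the plan says.** Protocol 8.8.5 sets the rule: "Each TEAE will further be attributed to a treatment (CST103/CST107 or placebo) based on the AE start date". A start date before the first Period 2 dose goes to the Period 1 treatment. For later dates, "If a TEAE start date is on/after to the first dose in Treatment Period 2, the AE will be attributed to the treatment received" (meaning the second-period treatment).

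The supporting definitions also work in dates. Protocol 6.1.2 lists the content of an AE report: "All reports should contain a brief description of the event, date of onset", then resolution date, severity and so on, with no onset time. SAP 6.1 defines treatment start as the date of first dose and adds: "Each treatment period will have a treatment start date (i.e., in order to determine AEs occurring during a treatment". SAP Appendix 1, which sets the treatment-emergent flag, compares one date with another and counts the same day as on treatment.

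Two other provisions work by sequence in time. SAP 10.1 attributes an AE to the treatment being received when it occurs, and states: "Events that occur during the washout period between Treatment Period 1 and 2 will be attributed to the treatment received in Period 1". Protocol 6.1.2 has the investigator judge the relationship "between each AE and the most recently administered study medication".

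**The concern.** Day 1 of Period 2 belongs partly to the washout and partly to the new period. Before the dose, the subject has vital signs and an ECG within 15 minutes of dosing (Protocol 5.1.1.3 and 5.1.2.3). The safety labs need an 8-hour fast, while dosing follows the first meal (Protocol 7.2), so the labs are pre-dose by inference. The schedule has no visit between Period 1 Day 14 and this one. These are therefore the only scheduled lab, ECG and vital-sign checks that can reveal a washout abnormality. For a symptomless finding, the date of the sample or tracing is usually the only onset date available (my inference; the documents do not define it).

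If such a finding becomes an AE dated that day, the date rule gives it to the Period 2 treatment. With two treatments, the other period is always the other treatment. A subject on the placebo-first sequence could have an AE tabulated under CST-103/CST-107 before ever taking it. An AE judged related to the Period 1 medication could appear in the related-AE table under the Period 2 treatment.

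**Working it through.** The documents give no figure for this point, so there is none to reproduce. The check applies the rules to cases, then sizes the effect under stated assumptions.

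**Step 1. Rules applied to four onsets.** The date rule compares the onset date with the date of first dose in the period. The time rule compares the onset date and time with the dose date and time.

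| Recorded onset | Date rule | Time rule |
|---|---|---|
| 3 days before Period 2 Day 1, reported at that visit | Period 1 | Period 1 |
| Period 2 Day 1, 1 hour before dose | Period 2 | Period 1 |
| Period 2 Day 1, 1 hour after dose | Period 2 | Period 2 |
| Period 1 Day 1, 1 hour before first dose | TEAE, Period 1 | Not a TEAE |

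The second row is the point at issue. The fourth shows the same gap at the start of Period 1.

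**Step 2. Boundary wordings side by side.** For treatment emergence, SAP 10.1 requires onset after the date of first dose. Read literally, that excludes all of Day 1, including post-dose events. SAP Appendix 1 includes the whole of Day 1. Protocol 8.8.5 uses on or after the first dose itself. These are three different boundaries.

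**Step 3. Number of AEs that change column.** From Protocol 8.1 and 7.2.1, N is about 40, randomized 1:1, so 20 per sequence. Assume that all enter Period 2 and that a share q has one new AE with pre-dose onset that day (q is not in the documents).

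AEs moved = 40 × q:
- q = 2.5%: 1
- q = 5%: 2
- q = 10%: 4
- q = 20%: 8

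If q is the same in both sequences, the expected number in each direction is 20 × q, so the expected net shift is zero.

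**Step 4. Unequal rates.** Let qA be the rate after active and qP the rate after placebo. Each treatment column has 40 subjects. Assume that affected subjects are not already counted in the same table row.

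- Contrast within this subset, active minus placebo, under SAP 10.1: (20·qA − 20·qP)/40.
- The same contrast under the date rule: (20·qP − 20·qA)/40.

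With qA = 10% and qP = 5% (assumed), 20 × 0.10 = 2 AEs move from active to placebo and 20 × 0.05 = 1 moves from placebo to active. Active changes by (1 − 2)/40 = −2.5 percentage points and placebo by +2.5. The subset contrast is −2.5 points instead of +2.5. At 10% versus 0%, each column moves by 20 × 0.10/40 = 5 points.

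**The case against.** The strongest reply is that the plan already intends the right answer. Protocol 8.8.5 cuts at the first Period 2 dose, not the first dosing day, so a pre-dose event could be read as prior to it. SAP 10.1 states the time-of-event principle and the washout rule. Appendix 1 governs the treatment-emergent flag, not attribution between periods. Protocol 6.1.2 says what a report should contain and does not exclude a time. The SAP rests on CRF version 6.0, which is not among the documents, so onset time may be captured. The study is descriptive, and all AEs are listed.

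Much of this stands. It makes the defect a conflict between provisions, not a plan fixed on the wrong principle. But the stated working variable is the start date, and SAP 6.1 gives a date for placing AEs in a period. A programmer following those provisions assigns the second case in the table to Period 2.

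A reader might go further and infer that every abnormality found at the pre-dose visit is misassigned and that the active-placebo AE comparison is reversed. The documents do not support that:
- Attribution follows onset, not detection, so events that began on an earlier washout day go to Period 1.
- Only clinically significant findings become AEs (Protocol 6.1.1). For labs, Protocol 6.2 also asks for symptoms or a change in concomitant therapy, although 6.1.2 is broader.
- The sign reverses only within this subset. The tables pool events from 14 dosing days plus washout or follow-up.
- No document shows a treatment-dependent excess at least 14 days after the last dose. Protocol 1.4.2.1 describes the hypokalemia seen in prior studies as transient or as recovering within hours.

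SAP 6.3 might also be cited as a direct contradiction, since "Baseline will be based on the last non-missing value collected prior to or on the treatment start date and time" uses a clock time. It defines baseline for measured values and does not govern AEs. It does show that dose time is available. Read by period, it allows one pre-dose value to be both the Period 2 baseline and the source of a Period 2 AE.

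**Conclusion.** The concern holds in a limited form. An AE with recorded onset on Period 2 Day 1 that arose before the dose is counted under the Period 2 treatment by the date rule, against SAP 10.1 and against the causality reference in Protocol 6.1.2. Calling that column wrong means wrong under the plan's own washout convention; it does not prove that the Period 1 treatment caused the event.

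The effect is likely to be 1 to 2 AEs, resting on an assumed 2.5% to 5% of about 40 subjects. A net bias in the comparison needs unequal rates after active and placebo, for which the documents give no evidence. Whether onset time is already collected cannot be settled from the documents. The change is still worth making, because one or two AEs are visible in tables this small and the remedy only carries out a rule that the SAP already states.

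**What to change.** In SAP 10.1 now, and in Protocol 8.8.5 at the next amendment, add a rule for AEs whose onset is dated on a Day 1 visit. Compare the onset time, or the time of the lab, ECG or vital sign that revealed the event, with the dose time, which SAP 7.7 already lists.

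- Pre-dose onset on Period 2 Day 1: attribute to the Period 1 treatment.
- Pre-dose onset on Period 1 Day 1: not treatment-emergent.
- Onset at or after the dose: attribute to that period's treatment.
- Time unknown: keep the date rule.

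If the AE form does not capture onset time, add a before/after-dose flag for Day 1 onsets. Align the boundary wording in SAP 10.1, SAP Appendix 1 and Protocol 8.8.5.

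The cost is a short SAP edit and possibly one form field, with no new assessments. The protocol wording touches two regional protocols (SAP 2.1) and needs ethics committee approval (Protocol 9.8), so it should wait for an amendment made for other reasons. AEs already recorded without a usable time will still follow the date rule.

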8.8.6. Concomitant Medications

Concomitant medications will be coded using the World Health Organization Drug Dictionary. Medications taken on or after the first day of the treatment period through the end of treatment will be considered on-treatment medications and will be summarized. All medications will be listed.

8.8.7. Study Drug Administration

Subject exposure to study drug and compliance will be summarized by treatment and treatment sequence. All study medication dispensed and returned, exposure, and compliance data will be listed.

8.8.8. Clinical Laboratory Results, Vital Signs, and ECGs

Absolute values and changes from baseline will be summarized by cohort, disease criteria, treatment and overall. In addition, clinical laboratory results and ECG shift tables may be generated.

All results will be listed. Laboratory values outside of normal ranges and clinically significant ECG abnormalities will be flagged.

8.8.9. Analysis Pharmacokinetic Endpoints

PK endpoints will be summarized by disease criteria, treatment and overall using the PKS. All PK endpoints will be listed.

Individual plasma CST-103 and CST-107 concentrations will be listed for each subject and summarized by nominal sampling timepoint with descriptive statistics (sample size [N], arithmetic mean, standard deviation, median, minimum, maximum, geometric mean and coefficient of variation). Individual and mean CST-103 and CST-107 concentration-time profiles will also be presented graphically on both a linear and log-linear scale.

All PK parameters will be computed from the individual plasma CST-103 and CST-107 concentrations using an appropriate noncompartmental or compartmental approach. The actual PK sampling timepoints will be used for the PK analysis if available, and there are significant deviations from the nominal collection times.

The PK parameters that may be determined (including C_{max} , t_{max} , AUC_t , AUC_{inf} , $t_{1/2}$) will be calculated.

Additional analyses will be performed as deemed necessary upon review of the data.

8.9. Analysis of Exploratory Endpoints

Absolute values and changes from baseline in inflammatory and neurodegenerative inflammatory biomarkers will be summarized by treatment and overall using the FAS.

Brain imaging signals in the locus coeruleus complex using neuromelanin-sensitive MRI sequence will be summarized.

Correlations between clinical and biomarker data, as well as other additional analyses, may be performed and will be defined further in the SAP.

All exploratory endpoints will be listed.

8.10. Analysis of Other Endpoints

Medical history, physical examination, C-SSRS, protocol deviations, screening clinical & cognitive scales (i.e., DSST, MHYS, MoCA, HADS, FOG-Q, and RBD1Q) will be listed.

9. ETHICAL, LEGAL AND ADMINISTRATIVE ASPECTS

9.1. Data Quality Assurance

The Sponsor or designee will conduct either an in-person or virtual site visit to verify the qualifications of each Investigator, according to Sponsor's or designee's applicable standard operating procedure, inspect the site facilities, and inform the Investigator of responsibilities and the procedures for ensuring adequate and correct documentation.

The Investigator is required to prepare and maintain adequate and accurate case histories designed to record all observations and other data pertinent to the clinical trial for each clinical trial subject. All information recorded on the CRFs for this clinical trial must be consistent with the subjects' source documentation (i.e., medical records).

